#### Protocol/Amendment No.: UVA-LACC-PD201, Version 4.0, 06 March 2018

Myocarditis	Grade 1 or 2 Grade 3 or 4	Withhold Permanently discontinue	•	Based on severity of AE administer corticosteroids	•	Ensure adequate evaluation to confirm etiology and/or exclude other causes
All other immune- related AEs	Intolerable/ persistent Grade 2 Grade 3 Grade 4 or recurrent Grade 3	Withhold or discontinue based on the type of event. Events that require discontinuation include and not limited to: Gullain-Barre Syndrome, encephalitis Permanently discontinue	-	Based on type and severity of AE administer corticosteroids	•	Ensure adequate evaluation to confirm etiology and/or exclude other causes

**NOTE:** For participants with Grade 3 or 4 immune-related endocrinopathy where withhold of pembrolizumab is required,

pembrolizumab may be resumed when AE resolves to ≤ Grade 2 and is controlled with hormonal replacement therapy or achieved metabolic control (in case of T1DM)

# 5.3.2.2 Dose Modifications of Other Treatments

## 5.3.2.3 Radiation Dose Modifications

Radiation treatment may be delayed due to toxicities for 1-7 consecutive days in patients in either treatment arm. Additionally, the start of brachytherapy can be delayed 1-14 days from completion of external beam RT if needed. All radiation treatments must be delivered within a total of 8 weeks, therefore treatment breaks should be kept to a minimum.

If radiation treatment is held, then cisplatin dose should be held until radiation treatment is resumed.

# 5.3.2.4 Cisplatin Dose Modifications

Toxicity due to cisplatin administration may be managed by symptomatic treatment, dose interruptions and adjustment of cisplatin dose. Recommended dose reductions are provided in Table 3. Dose should only be reduced once and future dosing should continue at the reduced dose. If the reduced dose cannot be tolerated the subject may continue on study without cisplatin (may continue to receive pembrolizumab and RT).

Table 3. Cisplatin Dose Modifications			
DOSE LEVEL CISPLATIN			
Dose Level 1	40 mg/m  (max = 70 mg*)		
Dose Level -1	30 mg/m  (max = 52.5 mg*)		
* Max doses apply to those with BSA > 1.75 m 			

Protocol/Amendment No.: UVA-LACC-PD201, Version 4.0, 06 March 2018

## 5.3.2.4.1 Recommendations for Cisplatin Dose Modifications

#### Gastrointestinal Adverse Effects

- For nausea and vomiting, anti-emetics should be used prophylactically.
- For Grade 4 nausea and vomiting, reduce Cisplatin by one dose level.

## Renal/Genitourinary Adverse Effects

- If creatinine rises to greater than 2.0 mg/dl, hold cisplatin therapy. If creatinine does not recover after a one-week delay, discontinue cisplatin for remainder of regimen.
- Selective renal tubular defects are sometimes observed:
  - Hypocalcemia with hypomagnesemia and hypokalemia are common and potentially severe.
  - o Replacement of magnesium, calcium and potassium are usually effective.
  - o Severe tubular effects, although rare, may require chronic replacement therapy.
  - Diagnostic tests for alternative mechanisms of hypocalcemia (e.g. GI or metabolic) should be considered.

## Neurologic Adverse Effects

- Grade 1 No change
- Grade 2 Reduce Cisplatin by one dose level
- Grade 3-4 Hold cisplatin. Reduce Cisplatin by one dose level after recovery to ≤ Grade 2

## Blood/Bone Marrow (Hematologic) Adverse Effects

- Cisplatin should be withheld from patients with an ANC less than 1,000 or platelet count less than 50,000. Therapy should be delayed week-by-week until these levels are exceeded. Any interruption in cisplatin for longer than one week due to toxicity requires a dose reduction of one level.
- External radiation should continue while drug is withheld.

## 5.3.3 Timing of Dose Administration

The below sections describe the recommended timing of study specific treatments. Treatments may be delayed up to 3 days (without this being considered to be a protocol violation) for major life events (e.g., serious illness in a family member, major holiday, vacation which is unable to be re-scheduled).

## 5.3.3.1 Cisplatin

Cisplatin chemotherapy will consist of weekly administrations of 40 mg/m^2 of cisplatin administered in 1 L of IV fluid (according to local protocol) delivered in 1 hour IV infusion (per institutional guidelines) The maximum dose of cisplatin administered should not exceed 70 mg. Cisplatin will be given on a day that IMRT is scheduled and must be given prior to radiation therapy that day. Cisplatin should be given on a Monday, Tuesday or Wednesday. Cisplatin infusion should proceed after all procedures/assessments have been completed as detailed on the Trial Flow Chart (Section 6.0).

# 5.3.3.2 Pembrolizumab

Pembrolizumab 200 mg will be administered as a 30 minute IV infusion every 3 weeks. Sites should make every effort to target infusion timing to be as close to 30 minutes as possible. However, given the variability of infusion pumps from site to site, a window of -5 minutes and +10 minutes is permitted (i.e., infusion time is 30 minutes: -5 min/+10 min).

Pembrolizumab should be administered on day of treatment after all pretreatment procedures/assessments have been completed as detailed on the Trial Flow Chart (Section 6.0). Trial treatment may be administered up to 3 days before or after the scheduled treatment date due to administrative reasons.

Pembrolizumab treatment to subjects in Arm 2 should be given prior to any other chemoradiation treatment (i.e. prior to radiation therapy). It is recommended that subjects receive pembrolizumab on the same day as cisplatin. The pembrolizumab infusion can be administered concurrent to the prehydration for the cisplatin treatment.

All trial treatments will be administered on an outpatient basis.

# 5.3.3.3 Radiation Treatments

Radiation therapy details will be identical for both Arms 1 and 2. This trial will include external beam radiation therapy (EBRT), including intensity modulated radiation therapy (IMRT), and image-guided brachytherapy with three-dimensional (3-D) treatment planning. IMRT is included as it may reduce the acute normal tissue toxicity from cervical cancer radiotherapy[14], and 3-D planned brachytherapy has been shown to improve local tumor control and reduce toxicity compared to two-dimensional planning.[15] Standard doses of external beam radiation therapy and brachytherapy will be delivered, and this radiation therapy section is written with the purpose of including the range of treatment approaches used by each participating institution, as long as the cumulative doses are within the target range. Each institution may follow their specific institutional policies for IMRT, including pseudo-split-field IMRT.[16] Parametrial boosts and nodal boosts may be delivered using either sequential or concomitant-integrated boost methods. Investigators may use both simultaneous and integrated boosts to comply with local institutional policies.[17] All IMRT and brachytherapy treatments must be delivered within a total of 8 weeks.

# 5.3.3.3.1 External Beam Radiation Therapy

IMRT planning is encouraged in this study. However, three-dimensional conformal radiation therapy is permitted instead of IMRT if cumulative organ-at-risk (OAR) constraints are respected. The EBRT plan will deliver at least 45 Gy, with treatment sites including the primary tumor and nodal volumes. Consensus guidelines are suggested to define target volume definition for IMRT.[18] This may be accompanied by parametrial or nodal boosts of 5.4-18 Gy as indicated (up to total dose of 63 Gy by EBRT). Three-dimensional conformal radiation therapy is permitted instead of IMRT if cumulative organ-at-risk (OAR) constraints are respected.

## Simulation and Immobilization

CT simulation is required for the study to permit target delineation and dose calculation. Patients may be simulated in the supine or prone position based on institutional practice. If a four-field, 3D conformal plan is used rather than IMRT, prone positioning with a belly board is recommended.

## Target Volume ad Organ-At-Risk Definitions

Target volumes and OARs must be defined on CT scan, and co-registered complementary imaging (i.e., MRI and/or PET imaging) can be used based on institutional practice. OAR volumes should include the entire organ (rather than just the wall of the organ) for ease of reporting. The radiation therapy case report forms will use the following nomenclature, so consistent labeling is suggested. *Investigators may choose to label structures differently according to institutional standards, and the target volume and OAR labeling are suggestions, not protocol requirements*. , When completing the case report forms, investigators are asked to simply report the requested data for their target volume that is most similar to the structures described below. The case report form will request the data using the following labels:

Target Volumes	Description			
GTV (gross tumor volume) or HR-CTV (high risk CTV)	Gross tumor alone (GTV) or gross tumor and highest risk area at time of brachytherapy (HR-CTV)			
GTVnodal	Gross tumor volume for lymph node as identified or imaging or exam. Dose to the nodal volume receivin highest boost dose will be requested.			
CTVnodal	Clinical target volume for regional lymph nodes. Prescription dose to at-risk nodal regions will be requested.			
OARs	Description			
Bladder	Entire organ contoured on CT. Cumulative dose from EBRT+brachytherapy will be requested.			
Sigmoid	Entire organ contoured on CT. Cumulative dose from EBRT+brachytherapy will be requested.			
Rectum	Contoured from ischial tuberosities to sigmoid flexur Entire organ contoured. Cumulative dose from EBRT+brachytherapy will be requested.			
Bowel	May be contoured as bag of bowel or individual loops of bowel. Cumulative dose from EBRT alone will be requested.			

CT = computed tomography; CTV = clinical target volume; EBRT = external beam radiation therapy; GTV = gross tumor volume

## Treatment Planning

IMRT or 3D conformal RT planning will be used to deliver a total dose of at least 45 Gy to the nodal CTV. Depending on institutional practice, pseudo-split-field IMRT or integrated boost approaches can be used with goal of meeting the planning objectives stated in the table below. The following

objectives are based on a recent RTOG protocol (NCT01672892), published series,[16, 17, 19] and guidelines.[20, 21]

Target Volumes	Planning Objectives			
GTV or HR-CTV	D90 EQD2 ≥ 80 Gy (representing dose from brachytherapy + EBRT)			
GTVnodal	≥ 59 Gy from EBRT			
CTVnodal	≥ 45 Gy from EBRT			
OARs	Planning Objectives			
Bladder	D2cc ≤ 90 Gy EQD2 (representing dose from brachytherapy + EBRT)			
Sigmoid	D2cc ≤ 75 Gy EQD2 (representing dose from brachytherapy + EBRT)			
Rectum	D2cc ≤ 75 Gy EQD2 (representing dose from brachytherapy + EBRT)			
Bowel	D5cc ≤ 55 Gy EQD2 (representing dose from EBRT only); no more than 30% receives 40 Gy			

D2cc = dose encompassing the highest exposed 2 cc; D5cc = dose encompassing the most exposed 5 cc; EQD2 = equivalent dose in 2 Gy fractions; HR-CTV = high risk clinical target volume (recommended to comply with GEC-ESTRO definition[21]); EBRT = external beam RT; OARs = organs at risk

## Treatment Delivery

Daily imaging is recommended during EBRT to permit verification of target alignment. Imaging and alignment method is to follow institutional practice, and can consist of orthogonal plain films, kV matching or CT imaging.

# 5.3.3.3.2 Brachytherapy

Brachytherapy will consist of 4-6 fractions of 5-7 Gy per fraction delivered with high-dose-rate (HDR) brachytherapy, based on institutional practice. Brachytherapy is not to be delivered on the same day as cisplatin chemotherapy.

Either CT-based or MRI-based treatment planning will be permitted for brachytherapy. The minimum EQD2Gy for the highest dose encompassing 90% (D90) of the high-risk clinical target volume (HR-CTV) or gross tumor volume (GTV) is 80 Gy, consistent with ABS guidelines.[20] It is recommended that the HR-CTV D90 is  $\geq$  100% of the prescription dose and the HR-CTV volume encompassing 100% of the target volume (V100) is  $\geq$  90%.

Cumulative doses to rectum, bladder, sigmoid and bowel will be followed to limit doses below threshold values for dose to the hottest 2 cc (D2cc) as calculated by equivalent dose in 2 Gy fractions (EQD2Gy) using a modified version of the American Brachytherapy Society (ABS) worksheet. The EQD2Gy limits will be 90 Gy for bladder and 75 Gy for rectum and sigmoid. This is consistent with ABS guidelines.[20]

#### Protocol/Amendment No.: UVA-LACC-PD201, Version 4.0, 06 March 2018

#### Brachytherapy Target Volume Definitions

It is recommended that the brachytherapy treatment planning include delineation of the GTV or HR-CTV, per institutional practice, as well as the rectum, sigmoid, bladder and bowel.

## Dose Reporting

Case report forms will request these doses for each fraction of brachytherapy: estimated D90 and V100 for the HR-CTV or GTV, Point A, and D2cc for sigmoid, rectum, bladder and bowel. Cumulative EQD2Gy doses for D90 of the HRCTV and D2cc for the sigmoid, rectum, bladder and bowel will be requested.

## 5.4 Concomitant Medications/Vaccinations

Medications or vaccinations specifically prohibited in the exclusion criteria and listed in Section 5.4.2 are not allowed during the Screening and Treatment Phase of this trial. There are no prohibited therapies during the Post-Treatment Follow-up Phase.

If there is a clinical indication for one of these or other medications or vaccinations specifically prohibited during the trial, discontinuation from trial therapy or vaccination may be required. The investigator should discuss any questions regarding this with the Sponsor-Investigator. The final decision on any supportive therapy or vaccination rests with the investigator and/or the subject's primary physician.

# 5.4.1 Acceptable Concomitant Medications

All treatments that the investigator considers necessary for a subject's welfare may be administered at the discretion of the investigator in keeping with the community standards of medical care.

## 5.4.2 Prohibited Concomitant Medications

Subjects are prohibited from receiving the following therapies during the Screening and Treatment Phase of this trial:

- Antineoplastic systemic chemotherapy or biological therapy
- Immunotherapy not specified in this protocol
- Chemotherapy not specified in this protocol
- Investigational agents other than pembrolizumab
- Radiation therapy not specified in this protocol
- Live vaccines
- Systemic glucocorticoids for any purpose other than to modulate symptoms from an event of clinical interest of suspected immunologic etiology. The use of physiologic doses of corticosteroids may be approved after consultation with the Sponsor-Investigator.

#### 5.5 Rescue Medications & Supportive Care

#### 5.5.1 Supportive Care Guidelines

Subjects should receive appropriate supportive care measures as deemed necessary by the treating investigator. Suggested supportive care measures for the management of adverse events with potential immunologic etiology are outlined below and in greater detail in the ECI guidance document. Where appropriate, these guidelines include the use of oral or intravenous treatment with corticosteroids as well as additional anti-inflammatory agents if symptoms do not improve with administration of corticosteroids. Note that several courses of steroid tapering may be necessary as symptoms may worsen when the steroid dose is decreased. For each disorder, attempts should be made to rule out other causes such as metastatic disease or bacterial or viral infection, which might require additional supportive care. The treatment guidelines are recommended when the investigator determines the events to be related to pembrolizumab.

Note: if after the evaluation the event is determined not to be related, the investigator is instructed to follow the ECI reporting guidance but does not need to follow the treatment guidance (as outlined in the ECI guidance document). Refer to Section 5.3.2 for guidelines regarding dosing delays and modifications.

It may be necessary to perform conditional procedures such as bronchoscopy, endoscopy, or skin photography as part of evaluation of the event. These procedures should be performed at the discretion of the investigator and are not mandated by the protocol. Suggested conditional procedures, as appropriate, can be found in the ECI guidance document.

## Pneumonitis:

- For Grade 2 events, treat with systemic corticosteroids. When symptoms improve to Grade 1 or less, steroid taper should be started and continued over no less than 4 weeks.
- For Grade 3-4 events, immediately treat with intravenous steroids. Administer additional anti-inflammatory measures, as needed.
   For Grade 3-4 events, or recurrent Grade 2 events, permanently discontinue Pembrolizumab.
- Monitor participants for signs and symptoms of pneumonitis
- Evaluate participants with suspected pneumonitis with radiographic imaging and initiate corticosteroid treatment
- Add prophylactic antibiotics for opportunistic infections in the case of prolonged steroid administration.

#### Myocarditis:

- o Ensure adequate evaluation to confirm etiology and/or exclude other causes
- o Administer corticosteroids based on severity of event

## Diarrhea/Colitis:

Subjects should be carefully monitored for signs and symptoms of enterocolitis (such as diarrhea, abdominal pain, blood or mucus in stool, with or without fever) and of bowel perforation (such as peritoneal signs and ileus).

If diarrhea/colitis occurs prior to initiation of pembrolizumab or can be attributed to the CRT treatment, then subjects should be advised to drink liberal quantities of clear fluids and will receive standard management for diarrhea with loperamide, low residue diet and Lomotil if needed. If sufficient oral fluid intake is not feasible, fluid and electrolytes should be substituted via IV infusion. For Grade 2 or higher diarrhea where colitis is suspected, consider GI consultation and endoscopy to confirm or rule out colitis.

If diarrhea/colitis occurs after subject has received any administration of pembrolizumab, then it is critically important to evaluate the subject for immune-related diarrhea/colitis. The diarrhea/colitis is likely to be immune-related if it has any of the following characteristics:

- Bloody or mucous stools
- Cramping
- occurs at a timepoint not typical for chemoRT (i.e., in first 2 weeks of treatment or after completion of external beam RT)

If the event meets these criteria, then it should be treated as follows:

- All subjects who experience diarrhea/colitis should be advised to drink liberal quantities of clear fluids. If sufficient oral fluid intake is not feasible, fluid and electrolytes should be substituted via IV infusion.
- For Grade 2 diarrhea/colitis that is felt to be possibly, probably, or likely related to investigational agent, administer oral corticosteroids consistent with the guidelines in the pembrolizumab lab. Current recommendation is to start at an initial dose of 1 to 2 mg/kg/day prednisone or equivalent.
- For Grade 3 or 4 diarrhea/colitis that is felt to be possibly, probably, or likely related to investigational agent and that persists > 1 week, treat with intravenous steroids followed by high dose oral steroids.
- Withhold pembrolizumab administration for moderate (Grade 2) or severe (Grade 3) colitis, and permanently discontinue pembrolizumab administration for life-threatening (Grade 4) colitis.
- When symptoms improve to Grade 1 or less, steroid taper should be started and continued over no less than 4 weeks.
- Type 1 diabetes mellitus (if new onset, including diabetic ketoacidosis [DKA]) or ≥ Grade 3 Hyperglycemia, if associated with ketosis (ketonuria) or metabolic acidosis (DKA)
  - For T1DM or Grade 3-4 Hyperglycemia
    - Insulin replacement therapy is recommended for Type I diabetes mellitus and anti-hyperglycemic in participants for Grade 3-4 hyperglycemia with evidence of Beta-cell failure.
    - Monitor participants for hyperglycemia or other signs and symptoms of diabetes.
    - Evaluate subjects with serum glucose and a metabolic panel, urine ketones, glycosylated hemoglobin, and C-peptide.
- Hypophysitis:

- For Grade 2 events, treat with corticosteroids. When symptoms improve to Grade 1 or less, steroid taper should be started and continued over no less than 4 weeks. Replacement of appropriate hormones may be required as the steroid dose is tapered.
- For Grade 3-4 events, treat with an initial dose of IV corticosteroids followed by oral corticosteroids. When symptoms improve to Grade 1 or less, steroid taper should be started and continued over no less than 4 weeks. Replacement of appropriate hormones may be required as the steroid dose is tapered.
- Monitor for signs and symptoms of hypophysitis (including hypopituitarism and adrenal insufficiency)

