## 5.3.2.1 Pembrolizumab Dose Modification

Modification of the dose of pembrolizumab is not allowed on this study. The dose of pembrolizumab can be delayed or withheld due to adverse events. Adverse events (both non-serious and serious) associated with pembrolizumab exposure may represent an immunologic etiology. Pembrolizumab must be withheld for drug-related toxicities and severe or life-threatening AEs as per **Error! Reference source not found.** below. See Section 5.5.1 and Events of Clinical Interest Guidance Document for supportive care guidelines, including use of corticosteroids.

Pembrolizumab should be administered once every 21 days for 3 cycles. If a delay in dosing is required per the guidelines in **Error! Reference source not found.**, then the dose may be delayed for up to 7 days. In case the toxicity does not resolve to Grade 0-1 or baseline within 7 days, the dosing on either the second or third cycle may be withheld. If the second cycle dose cannot be administered due to unresolved toxicity, then the third dose of pembrolizumab should occur on the scheduled day 1 of the third cycle (if the toxicity has resolved to Grade 0-1 or baseline). If the third dose cannot be administered due to unresolved toxicity within 7 days, then the subject may continue on study without additional pembrolizumab (may continue to receive cisplatin and RT). In general, please follow the following pembrolizumab-specific guidelines:

- i. Corticosteroid taper should be initiated upon AE improving to Grade 1 or less and continue to taper over at least 4 weeks. This criterion may also be met if the toxicity resolves to pre-study baseline grade (if toxicity was present at baseline).
- ii. For severe and life-threatening irAEs, IV corticosteroid should be initiated first followed by oral steroid. Other immunosuppressive treatment should be initiated if irAEs cannot be controlled by corticosteroids.
- iii. For situations where pembrolizumab has been withheld and the toxicity has not resolved within 7 days, the dose may be skipped. Otherwise, pembrolizumab can be resumed after AE has been reduced to Grade 1 or 0 (or baseline, as described in "i") and corticosteroid has been tapered.

Immune-related AEs	Toxicity grade or conditions (CTCAEv4.0)	Action taken to pembrolizumab	irAE management with corticosteroid and/or other therapies	Monitor and follow-up

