Pneumonitis	Grade 2	Withhold	Administer corticosteroids (initial dose of 1-2 mg/kg prednisone or	
 
Monitor participants for signs and symptoms of pneumonitis
 
Evaluate participants with suspected pneumonitis with
 

	Grade 3 or 4, or recurrent Grade 2 Permanently discontinue by taper	
 
radiographic imaging and initiate corticosteroid treatment
 
Add prophylactic antibiotics for opportunistic infections
 
		
Diarrhea / Colitis	Grade 2 or 3	Withhold	Administer corticosteroids (initial dose of 1-2 mg/kg prednisone or equivalent) followed by taper	
 
Monitor participants for signs and symptoms of enterocolitis (ie, diarrhea, abdominal pain, blood or mucus in stool with or without fever) and of bowel perforation (ie, peritoneal signs and ileus).
 

Table 3. Dose Modification and Toxicity Management Guidelines for Immune-related AEs Associated with Pembrolizumab

AST / ALT	Grade 4 Grade 2	Permanently discontinue Withhold	Administer	
 
Participants with ≥ Grade 2 diarrhea suspecting colitis should consider GI consultation and performing endoscopy to rule out colitis.
 
Participants with diarrhea/colitis should be advised to drink liberal quantities of clear fluids. If sufficient oral fluid intake is not feasible, fluid and electrolytes should be substituted via IV infusion.
 
Monitor with liver function tests
 

elevation or Increased bilirubin			corticosteroids (initial dose of 0.5- 1 mg/kg prednisone or equivalent) followed by taper	(consider weekly or more frequently until liver enzyme value returned to baseline or is stable
	Grade 3 or 4	Permanently discontinue	Administer corticosteroids (initial dose of 1-2 mg/kg prednisone or equivalent) followed by taper	
Type 1 diabetes mellitus (T1DM) or Hyperglycemia	Newly onset T1DM or Grade 3 or 4 hyperglycemia associated with evidence of β- cell failure	Withhold	
 
Initiate insulin replacement therapy for participants with T1DM
 
Administer anti- hyperglycemic in participants with hyperglycemia
 
	
 
Monitor participants for hyperglycemia or other signs and symptoms of diabetes.
 

Hypophysitis	Grade 2 Grade 3 or 4	Withhold Withhold or permanently discontinue 	Administer corticosteroids and initiate hormonal replacements as clinically indicated.	
 
Monitor for signs and symptoms of hypophysitis (including hypopituitarism and adrenal insufficiency)
 

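### Section 5.5.1 ties steroids for pembrolizumab-related Grade 3-4 diarrhea/colitis to persistence beyond one week, while the immune-related AE table (Grade 3) and Section 5.3.2.1 rule ii state no wait

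*Combined protocol and SAP*

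**What the plan says.** The Diarrhea/Colitis entry of Section 5.5.1 first separates diarrhea attributable to chemoradiation, which gets standard antidiarrheal management. It then lists features that make an immune cause likely: blood or mucus in the stool, cramping, or onset at a time unusual for chemoradiation. For events with any of these features it gives steroid rules by grade:

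- Grade 2: "For Grade 2 diarrhea/colitis that is felt to be possibly, probably, or likely related to investigational agent, administer oral corticosteroids", starting at 1 to 2 mg/kg/day of prednisone or equivalent.
- Grade 3 or 4: the event must be at least possibly "related to investigational agent and that persists > 1 week, treat with intravenous steroids", followed by high-dose oral steroids.

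Three other texts bear on the same decision:

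- The immune-related AE table in Section 5.3.2.1 (the first of two tables numbered 3), diarrhea/colitis, Grade 2 or 3: "Administer corticosteroids (initial dose of 1-2 mg/kg prednisone or equivalent) followed by taper".
- Section 5.3.2.1, rule ii: "For severe and life-threatening irAEs, IV corticosteroid should be initiated first followed by oral steroid".
- The introduction to Section 5.5.1: "The treatment guidelines are recommended when the investigator determines the events to be related to pembrolizumab".

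Section 5.3.2.1 also sends sites to 5.5.1 for this purpose: "See Section 5.5.1 and Events of Clinical Interest Guidance Document for supportive care guidelines, including use of corticosteroids".

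**The concern.** The persistence clause makes the rule for the more severe event slower than the rule for the milder one. A site that follows 5.5.1 as written gives oral steroids for related Grade 2 colitis without delay, but finds no steroid instruction for related Grade 3 or 4 colitis until it has lasted more than a week. A site that follows the table or rule ii meets no such wait.

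The trial is multi-center and safety is a primary objective. The same entry tells sites to watch for bowel perforation and treats evaluation for immune-related colitis as critical. Conflicting instructions could therefore lead sites to manage the same event differently, and one literal reading delays treatment of severe immune colitis by a week.

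**Working it through.** No formula applies. The check compares the steroid instructions and the wait that each one states.

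**1. Which events the clause covers.** The Grade 3-4 bullet applies only after the event has met the immune-cause features, and it separately requires relatedness to pembrolizumab. Diarrhea attributed to chemoradiation has already been routed elsewhere. The one-week condition is therefore an addition to the attribution step.

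**2. Stated wait before steroids.**

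| Text | Events covered | Wait stated |
|---|---|---|
| 5.5.1 Diarrhea/Colitis | Grade 3-4, related | More than 7 days |
| 5.5.1 Diarrhea/Colitis | Grade 2, related | None |
| Immune-related AE table, 5.3.2.1 | Diarrhea/colitis, Grade 2 or 3 | None |
| 5.3.2.1 rule ii | Severe and life-threatening immune-related AEs | None |
| 5.5.1 Pneumonitis | Grade 3-4 | None: "For Grade 3-4 events, immediately treat with intravenous steroids" |
| 5.5.1 Hypophysitis | Grade 3-4 | None |
| 5.5.1 Hepatic | Grade 2-4 | None |
| 5.5.1 Renal failure or nephritis | Grade 2-4 | None |

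**3. Comparison by grade.**

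- Grade 3: 5.5.1 conflicts directly with the table, which gives corticosteroids without a duration condition. It is also inconsistent with rule ii.
- Grade 4: 5.5.1 is inconsistent with rule ii. Nothing is claimed from the table here, because its Grade 4 colitis row cannot be read reliably in the available text.
- Grade 2 against Grade 3-4, within 5.5.1: the order of urgency is reversed.

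**4. Size of the gap.** For an event that starts at Grade 3-4, the literal difference is about 7 − 0 = 7 days. For one that passes through Grade 2 it is shorter, because oral steroids may already have begun.

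**5. Comparison with other organs.** Of the four other 5.5.1 entries tabulated, 0 of 4 sets a duration condition. Grade 3-4 hyperthyroidism and myocarditis also have steroid instructions without a wait, so including them gives 0 of 6.

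**6. Reconciling text.** No passage says that one text overrides another, or that the table gives initial treatment and 5.5.1 gives escalation.

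**The case against.** The strongest defense has five parts.

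- **Guidance only.** Section 5.5.1 calls its measures suggested and nowhere says to withhold steroids in the first week. Section 5.4.2 exempts immune events from its steroid prohibition, which covers "Systemic glucocorticoids for any purpose other than to modulate symptoms from an event of clinical interest of suspected immunologic etiology". Sections 5.4 and 5.4.1 leave supportive therapy to the treating physician, and a separate guidance document on events of clinical interest may give more detail. All of this stands, and it limits the likely harm. It does not settle which text a site should follow, and that guidance document is not available here.
- **Start, then escalate.** The table could be read as initial treatment for Grade 3, with 5.5.1 as escalation if the event persists. That would be coherent, but the protocol does not say it.
- **Rule ii sets the order of routes, not timing.** Its point is intravenous before oral, and it sits in a list of general guidelines. It is fair to say that rule ii is silent on waiting rather than opposed to it. The Grade 4 comparison with another section therefore rests on a weaker text than the Grade 3 comparison.
- **Chemoradiation confounds bowel events.** Pelvic radiation and cisplatin cause gastrointestinal toxicity, cramping alone meets the immune-cause features, and Section 7.4.1 excludes Grade 3 colitis lasting less than 7 days from the dose-limiting toxicities. But attribution is handled before the steroid bullets apply, Grade 2 events pose the same problem and have no wait, and the 7.4.1 exception classifies events rather than governing treatment.
- **The remedy changes more than timing.** Without the clause, 5.5.1 would give intravenous steroid to every qualifying Grade 3 event, whereas the table names no route. That is correct. The result agrees with the table on timing and with rule ii on route, so the remedy remains sound.

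**Conclusion.** The concern holds and should be corrected. For related Grade 3-4 diarrhea/colitis, 5.5.1 states a wait of more than 7 days that appears in none of the other texts compared. The conflict is direct for Grade 3. For Grade 4 it rests on rule ii and on the section's own Grade 2 bullet.

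The size is a literal delay of about 7 days per affected patient. It assumes that a site follows 5.5.1 as written, that the event begins at Grade 3-4, and that the unseen guidance document does not instruct otherwise. Sample size, error rates and planned analyses are unaffected.

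**What to change.** In the Grade 3-4 bullet of Section 5.5.1, Diarrhea/Colitis, delete the clause that requires persistence beyond one week. Steroids then start once the event is judged at least possibly related to pembrolizumab, which is in line with the relatedness trigger in the section's introduction.

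If the sponsor does intend a wait, the alternative is to state the same timing in 5.5.1, the table and rule ii. It would then also need to explain why Grade 2 is treated sooner.

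The cost is a protocol wording amendment that removes one clause.
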